## 4. PARTICIPANT ENTRY

The present project consists of a pilot observational study on patients diagnosed with brain tumours candidate for a neurosurgical operation.

Patients will be recruited following the inclusion criteria: any patient with a diagnosis of brain tumour, age ranging from 18 with no upper limit, who will agree to the operation and to take part of the present study, will be enrolled.

The present study will include:

- In vivo microscopic and/or endoscopic multispectral/hyperspectral analysis;
- In vivo microscopic and/or endoscopic fluorescence (using either infrared light - IR - or ultraviolet light, depending on the clinical indication of the specific case);

- In vivo microscopic and/or endoscopic fluorescence combined with multispectral/hyperspectral analysis.

Enrolment will proceed for 3 years, with the possibility of stopping the research at an earlier date if a sufficient amount of data is collected for a reliable statistical analysis. From a practical point of view, participation in the study will only imply that some images will be acquired during surgery and processed at a later stage. The study won't impact on patients' care at any stage, nor will produce results that will be relevant for future medical records of patients enrolled. Patients will be approached about this study at the time of their first neuro-oncology clinic consultation – this might not necessarily be the clinic where the diagnosis will be given for the first time, as these patients are often referred from other centres where the diagnosis has already been communicated. A member of the research team who is also involved in direct care will be present at the time of the consultation and will explain in details what are the purposes and the methods of the present study. The patient will be given a PIS at this point.

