Surgery will be conducted following standard procedures, already validated in clinical practice. The surgeons performing the procedures will be [name] [name] (CI), [name] (PhD student and clinical fellow), [name] (Consultant Neurosurgeon), and [name] (Neurosurgery Trainee and Clinical Lecturer). Surgeons will work in teams, each team with no more than two surgeons. [name] and one of his collaborators will be present in theatre to facilitate images acquisition. For each researcher not normally involved in clinical practice, research passport will be provided. Intra-operative imaging data and spectra will be collected during tumour resection, but the analysis on the spectra will be performed on a different time and setting, in order not to excessively prolong the surgical procedure.

Researchers will collect spectral data up until the statistical model used for multivariate analysis does not longer improve the degree of accuracy (see Section 6 - statistical analysis).

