## 6.1. FIRST AIM

*Detect structural differences between brain tumour tissue and surrounding brain.*

The Regions Of Interest (ROI) for multispectral/hyperspectral acquisition will be delineated on both peri-operative images (MRI scan) and intra-operative images as extrapolated from the intra-operative videos. We will focus our analysis on three main regions:

- normal brain tissue - brain tissue not infiltrated by tumour or edema, nor grossly pathological on pre-operative images or intra-operative images;
- suspected infiltrated brain tissue – tissue surrounding the tumour where there is strong radiological and clinical suspicion of infiltrative disease or edema;
- tumour tissue – margins and core of the tumour on pre-operative images and intra-operative findings.

The signal in one region of the tumour will be compared to a neighbouring 'healthy' region. The signal itself will come from a processed set of images of the brain, where we will fit the data using one of our established models to extract an indication of tissue oxygenation (as a %) on a per-pixel basis.

The comparison between the set of readings obtained from normal brain will be performed using Principal Component Analysis (PCA) and Linear Discriminant Analysis (LDA) or more advanced techniques including, for example, machine learning. Statistics will be collected on accuracy, sensitivity, specificity, ROC analysis.

We will also need to take pictures and/or videos of the surgical field in order to correlate the expected anatomical location of the tumour and infiltrated areas with the intra-operative finding. The surgical field is limited to the area under the microscope or endoscope

magnification, therefore no identifiable pictures or videos will be taken at any point during the study.

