### 6.3. THIRD AIM

*Test whether the combination of multispectral/hyperspectral analysis and fluorescence could provide useful new insight into the detection of different perfusion patterns of brain tumours VS normal brain tissue*

Multispectral/hyperspectral imaging will be tested to check whether it can increase the distinction of the fluorophore signal compared with the background. Dedicated statistical software will be used for this analysis.

Each image set will be analysed separately because there will be variability between patients and we will not be able to fully account for this with the limited number of datasets that we are going to record (a well-known problem with many biophotonics/optical techniques). This will all be done offline after the surgery is complete, with a primary aim is to observe whether the technique is capable of detecting changes in the tissue.

We will collect spectral data up until the statistical model used for multivariate analysis does not longer improve the degree of accuracy. We will aim to recruit approximately 50 patients with diagnosis of neuro-oncological disease. Each patient will have an average acquisition of 6 datasets. As each dataset will correspond to an image, this will be divided into many reading regions (from 10 to 20) for a total of approximatively 60 measurements per patient. Based on this estimation, we approximate that 50 patients will provide a spectral database of 3.000 spectra, which we calculate is adequate for diagnostic validation purposes [14].

Same tests as section 6.1 will be run to statistically validate the data.

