## 10. PUBLICATION POLICY

This study will follow the Imperial College of London publication policies and anti-plagiarism guidelines. Non-identifiable data will be used during publication. Authorships and authors order will be defined in due course. We will collect spectral data up until the statistical model used for multivariate analysis does not longer improve the degree of accuracy.

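### Section 6.3 rests its adequacy claim on 3,000 readings nested within 50 patients, without a precision target, a within-patient correlation or a stated unit of analysis, so adequacy is not shown

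*Combined protocol and SAP*

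**What the plan says.** The size statement is in section 6.3 (Third aim). About 50 patients are planned, with on average 6 datasets each and one image per dataset. Of each image the plan says "this will be divided into many reading regions (from 10 to 20) for a total of approximatively 60 measurements per patient". It concludes that "we approximate that 50 patients will provide a spectral database of 3.000 spectra, which we calculate is adequate for diagnostic validation purposes", citing reference 14. By its title, that reference concerns forecasting the sample size a classifier needs. None of its inputs or outputs is carried into the plan.

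The same section also says "Each image set will be analysed separately because there will be variability between patients and we will not be able to fully account for this", and describes the offline work by saying that "a primary aim is to observe whether the technique is capable of detecting changes in the tissue". The term image set is not defined.

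Section 6.1 specifies PCA with LDA, or machine learning, and adds "Statistics will be collected on accuracy, sensitivity, specificity, ROC analysis". Sections 6.2 and 6.3 refer back to the same tests. Section 3 calls the study a pilot.

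There is a second basis for size, stated in sections 4.1, 6.3 and 10: "Researchers will collect spectral data up until the statistical model used for multivariate analysis does not longer improve the degree of accuracy". Section 4 adds that enrolment runs for three years, "with the possibility of stopping the research at an earlier date if a sufficient amount of data is collected for a reliable statistical analysis".

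**The concern.** The adequacy claim is attached to a count of readings. Regions cut from one image, and images from one patient, share the tissue, the tumour, the lighting and the optical set-up. If correct and incorrect classifications cluster by patient, pooled readings carry less information than their number suggests.

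Section 6.3 itself gives reason to ask. It recognises variability between patients and responds by analysing image sets separately, yet it credits a single database of 3,000 spectra with diagnostic validation. A reader cannot tell which results would draw on that database.

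Two things are at stake:

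- **Precision.** Intervals for pooled accuracy, sensitivity, specificity or AUC that treat 3,000 readings as independent would be too narrow if readings correlate positively within patients.
- **The plateau rule.** Accuracy governs when data collection ends, but the plan does not say on which data it is measured or whether patients are kept intact in that evaluation. If one patient's readings fell in both training and test data, collection could stop on an accuracy that does not carry over to new patients.

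**Working it through.** **1. The plan's own count.** Inputs from section 6.3: 50 patients, 6 images per patient, 10 to 20 regions per image.

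- At 10 regions: 6 × 10 = 60 per patient, and 60 × 50 = 3,000. This reproduces the stated figures.
- At 20 regions: 6 × 20 = 120 per patient, and 120 × 50 = 6,000.

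The count is correct at the lower end of the stated range. The adequacy statement cannot be reproduced, because no target accuracy, precision, class split, learning-curve input or correlation is given.

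**2. What 3,000 means if data are pooled.** With equal clusters of m readings, the design effect is DE = 1 + (m − 1) × ICC, and the effective number is the total divided by DE. The ICC here is that of the correct/incorrect result within a patient. The documents give none, so a range is assumed. For m = 60:

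| ICC (assumed) | DE | 3,000 / DE |
|---|---|---|
| 0 | 1 | 3,000 |
| 0.01 | 1.59 | 1,887 |
| 0.1 | 6.9 | 435 |
| 0.3 | 18.7 | 160 |
| 0.5 | 30.5 | 98 |

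Only the first row gives the plan's number.

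**3. Illustrative precision for a pooled sensitivity.** Assumed: sensitivity 0.85, 50 patients, 20 tumour readings each (n = 1,000), a fixed classifier. Half-width = 1.96 × √(0.85 × 0.15 × DE / n), with DE = 1 + 19 × ICC. The next column repeats this with 40 readings each (n = 2,000, DE = 1 + 39 × ICC). The last column assumes 25 patients with 20 readings each (n = 500). Aim 2 is confined to monitored or awake patients, and their number is not stated.

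| ICC (assumed) | 50 patients × 20 | 50 patients × 40 | 25 patients × 20 |
|---|---|---|---|
| 0 | 2.21 | 1.56 | 3.13 |
| 0.01 | 2.41 | 1.85 | 3.41 |
| 0.05 | 3.09 | 2.69 | 4.37 |
| 0.1 | 3.77 | 3.46 | 5.33 |
| 0.3 | 5.73 | 5.58 | 8.10 |
| 0.5 | 7.17 | 7.09 | 10.14 |

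Entries are percentage points. A beta-binomial simulation (20,000 runs, 50 patients × 20) gave 2.43, 3.09, 3.81, 5.75 and 7.14 at ICC 0.01 to 0.5, in agreement with the formula.

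**4. More readings or more patients.** For 50 patients, going from 20 to 40 readings gains 5.73 − 5.58 = 0.15 points at ICC 0.3, but 2.414 − 1.845 = 0.57 points at ICC 0.01. Doubling patients instead (100 × 20) divides the half-width by √2: 5.73 / √2 = 4.05 at ICC 0.3, and 2.41 / √2 = 1.71 at ICC 0.01. At ICC 0.01 extra readings therefore help almost as much as extra patients. At ICC 0.3 they add little.

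**5. If image sets are analysed alone.** One image holds 10 to 20 of the reading regions counted in section 6.3, and one patient's images hold 60 to 120. Section 6.1 also derives oxygenation per pixel, so the region count need not be the number of data points in such an analysis. Either way, the 3,000 accumulated over 50 patients does not describe the precision of a result from one image set.

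**The case against.** The strongest reply is that the plan already deals with patient variability. Section 6.1 compares a tumour region with a neighbouring region judged healthy, and section 6.3 analyses image sets separately. In such a contrast, a patient effect common to both regions cancels, and the one-class design effect above does not describe it. This stands for within-image comparisons, so it would be wrong to infer that the plan ignores clustering. It does not carry over to a validation claim resting on a pooled database, and the plan does not say which results are of which kind.

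Second, a calculation may exist behind reference 14. That also stands: the documents allow the conclusion that adequacy is not shown, and no more.

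Third, no passage proposes splitting training and test data by reading. A reader might infer from the plateau rule that one is planned. The documents are silent, so the optimism described above is a risk left open and not a stated procedure.

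Fourth, this is a pilot with no precision target, so no half-width above fails a stated requirement. That is true, and it is also why a claim of diagnostic validation goes further than the plan supports. Section 6.3 speaks of observing whether changes can be detected, and the primary outcome in section 3.1 is the analysis of spectroscopic readings.

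**Conclusion.** The concern holds in a limited form. The adequacy statement in section 6.3 rests on a count of nested readings. That count is the effective sample size for pooled results only under independence within patients, which the plan neither states nor supports. The unit of analysis is unclear, and the accuracy behind the plateau rule has no stated patient-level evaluation.

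The size depends on an unknown ICC. In the 50 × 20 illustration the half-width grows from 2.2 points under independence to 2.4 at ICC 0.01, which is negligible, and to 5.7 at 0.3 and 7.2 at 0.5, which is about threefold. The sensitivity, readings per class, equal cluster sizes, fixed classifier and the 25 patients for Aim 2 are all assumptions.

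Two stronger readings are tempting and not supported. One is that 50 patients are too few: there is no target against which to judge that. The other is that only the number of patients matters for precision: step 4 shows that this fails at low ICC.

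This should be corrected before results are reported. Confidence is high that adequacy is not shown. How much precision is lost is unknown.

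**What to change.** **In section 6.3**, replace the adequacy statement. Give the size as about 50 patients contributing about 3,000 readings (up to 6,000 at 20 regions per image) that may be correlated within patient, with results reported as pilot estimates. Add the expected precision by number of patients over a stated range of ICCs, on the sponsor's own assumptions. Do this separately for Aim 2, using the expected number of monitored or awake patients.

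**In sections 6.1 to 6.3**, define image set and state which results are within an image set and which are pooled. Label results from a single image set as within-image, not as validation across patients.

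**Wherever patients are pooled**, including for the accuracy used in the plateau rule (sections 4.1, 6.3 and 10), keep all readings of a patient on one side of any training/test or cross-validation split. Compute intervals by a method that treats the patient as the cluster, for example by resampling whole patients.

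**Cost:** changes of wording and slightly more analysis work, with no extra patients or acquisitions. The stated precision may look less favourable, and the diagnostic-validation wording is lost.

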### 7. FURTHER DEVELOPMENT

This technology is completely novel, and in our estimation, it has the potential of changing the neuro-oncological surgery practice. Our hypothesis is that it could effectively

detect differences between brain and tumour tissues. Therefore, the present study could ultimately become a benchmark for the development of a new tool to guide the surgeon during brain tumours resection. It would also provide the community with more knowledge and understanding of the functional anatomy of the brain. More specifically, it could increase our knowledge of the vascular re-arrangement, structure, and oxygenation of brain tumours, as well as additional knowledge about perfusion and oxygen extraction in the brain between eloquent and non-eloquent areas – thus representing an intra-operative equivalent of a functional MRI, but without the same intra-operative hindrance and costs.

## 8. REGULATORY ISSUES

### 8.1. ETHICS APPROVAL

The Study Coordination Centre has obtained approval from the Research Ethics Committee (REC) and Health Regulator Authority (HRA). The study must also receive confirmation of capacity and capability from each participating NHS Trust before accepting participants into the study or any research activity is carried out. The study will be conducted in accordance with the recommendations for physicians involved in research on human subjects adopted by the 18th World Medical Assembly, Helsinki 1964 and later revisions.

### 8.2. CONSENT

Consent to enter the study must be sought from each participant only after a full explanation has been given, an information leaflet offered and time allowed for consideration. Signed participant consent should be obtained. The right of the participant to refuse to participate without giving reasons must be respected. After the participant has entered the study the clinician remains free to give alternative treatment to that specified in the protocol at any stage if he/she feels it is in the participant's best interest, but the reasons for doing so should be recorded. In these cases the

participants remain within the study for the purposes of data analysis. All participants are free to withdraw at any time from the protocol treatment without giving reasons and without prejudicing further treatment.

### **8.3. CONFIDENTIALITY**

The Chief Investigator will preserve the confidentiality of participants taking part in the study and is registered under the Data Protection Act.

There are two sets of data the researchers will collect:

- 1) Intra-operative images / videos and spectroscopic data;
- 2) Clinical data: diagnosis, clinical status, medical background, radiological, histopathological data, treatment data.

Regarding intraoperative multispectral data collection, these will be stored mostly on College Computers, and recording devices. Anonymous video recording and/or images acquisition will be carried out by the clinicians in order to sync spectral data collected with the surgical procedure. Each patient will be given a specific protocol number – Log ID. These data will be in pseudo-anonymized form when transferred to College Computers, and the images and videos will be coded using the specific protocol number / log ID previously assigned.

Regarding clinical data, these will be stored on NHS Trust Encrypted computers in a semi-anonymized form, and transferred on College Computers in a pseudo-anonymized form. NHS computers follow NHS Trust and Imperial College confidentiality policy. Semi-anonymization means that these data will include NHS number, Hospital Number, age, protocol number. No additional identifiable personal data – such as telephone numbers, address, name, and surname – will be stored, except for those on the copies of the consent forms for the Trial Master Files (TMF). These will be stored in a safe and restricted environment in CXH 3S (offices). Pseudo-anonymization will be performed prior to transfer clinical data to the College computers. Pseudo-anonymization means that these data will NOT include any identifiable information, including NHS number and hospital number. Only the protocol number / log ID will be included in the data stored on College Computers.

The following clinical data will be stored on College Computers: diagnosis, medical background, histological and radiological data, treatment data, intra-operative images and/or videos, spectroscopic data.

Electronic Transfer by magnetic or optical media, email or computer networks, use of audio/video recording devices, storage of personal data will be undertaken by the researchers who are also clinical care team responsible for direct care, at CXH. Pseudo-anonymized data will be transferred to the University computers by the clinical researchers and will be processed by College researchers either on College Computers in SK, SMH or HH.

In case a participant, who has given informed consent, loses capacity to consent during the study, the participant would be withdrawn from the study. Identifiable data or tissue already collected with consent would be retained and used in the study. No further data or tissue would be collected or any other research procedures carried out on or in relation to the participant.

Signed consent forms will be archived inside the patients' medical records and will be available for any audit and research quality control activities. Any identifiable data will be kept under Imperial College policy for 10 years including the consent form and the coded list. Patients will be given a copy of the signed consent form. A manual copy of the consent form will be retained in the Trial Master File (TMF) ONLY. No other copies will be done or retained.

#### **8.4. INDEMNITY**

**Imperial College London holds negligent harm and non-negligent harm insurance policies which apply to this study.**

#### **8.5. SPONSOR**

Imperial College of London will act as the main Sponsor for this study. Delegated responsibilities will be assigned to the NHS trusts taking part in this study.

## 8.6. FUNDING

Brain Tumour Research (BTR) charity is funding this study.

## 8.7. AUDITS

The study may be subject to inspection and audit by Imperial College London under their remit as sponsor and other regulatory bodies to ensure adherence to GCP and the UK Policy Frame Work for Health and Social Care Research.

## 10. PUBLICATION POLICY

This study will follow the Imperial College of London publication policies and anti-plagiarism guidelines. Non-identifiable data will be used during publication. Authorships and authors order will be defined in due course. We will collect spectral data up until the statistical model used for multivariate analysis does not longer improve the degree of accuracy.

## 11. GANTT CHART

TASK	01/20	04/20	07/20	10/20	01/21	04/21	07/21	10/21	01/22	04/22	7/22	10/22
Ethics approval	█	█										
Recruitment		█	█	█	█	█	█	█	█	█	█	█
Data analysis and write up										█	█	█

